#### **7.3.2.3 Severity of AEs**

The intensity/severity of AEs will be graded as follows:

- **Mild:** an AE, usually transient, which causes discomfort but does not interfere with the subject's/patient's routine activities
- **Moderate:** an AE which is sufficiently discomforting to interfere with the subject's/patient's routine activities
- **Severe:** an AE which is incapacitating and prevents the pursuit of the subject's/patient's routine activities

The grading of an AE is up to the medical judgement of the Investigator and will be decided on a case-by-case basis.

#### **7.3.2.4 Causality of AEs**

The relationship of AEs to the administered IMP will be assessed by the Investigator:

- **Probable:** reports including good reasons and sufficient documentation to assume a causal relationship, in the sense of plausible, conceivable, likely, but not necessarily highly probable. A reaction that follows a reasonable temporal sequence from administration of the IMP; or that follows a known or expected response pattern to the suspected medicine; or that is confirmed by stopping or reducing the dosage of the medicine and that could not reasonably be explained by known characteristics of the subject's/patient's clinical state.
- **Possible:** reports containing sufficient information to accept the possibility of a causal relationship, in the sense of not impossible and not unlikely, although the connection is uncertain or doubtful, for example because of missing data or insufficient evidence. A reaction that follows a reasonable temporal sequence from administration of the IMP; that follows a known or expected response pattern to the suspected medicine; but that could readily have been produced by a number of other factors.
- **Unlikely:** reports not following a reasonable temporal sequence from IMP administration. An event which may have been produced by the subject's/patient's clinical state or by environmental factors or other therapies administered.
- **Not related (unrelated):** events for which sufficient information exists to conclude that the aetiology is unrelated to the IMP.
- **Unclassified:** reports which for one reason or another are not yet assessable, e.g., because of outstanding information (can only be a temporary assessment).

### **7.3.2.5 Classification of ADRs by Expectedness**

ADRs will be classified by the Sponsor as either expected or unexpected:

- **Expected:** an ADR that is listed in the current edition of the Investigator's Brochure or other reference safety information.
- **Unexpected:** an ADR that is not listed in the current edition of the Investigator's Brochure or other reference safety information, or that differs because of greater severity or greater specificity.

### **7.3.2.6 Outcome of AEs**

The outcome of all reported AEs has to be documented as follows:

1. Recovered, resolved
2. Recovering, resolving
3. Not recovered, not resolved
4. Recovered, resolved with sequelae
5. Fatal
6. Unknown

**NOTE:** A subject's/patient's **death** per se is not an event, but an outcome. The event which resulted in the subject's/patient's death must be fully documented and reported, even in case the death occurs within 4 weeks after IMP treatment end and regardless of whether or not it is considered treatment-related.

### **7.3.2.7 Action(s) taken**

AEs requiring action or therapy must be treated with recognised standards of medical care to protect the health and wellbeing of the subject/patient. Appropriate resuscitation equipment and medicines must be available to ensure the best possible treatment in an emergency situation.

The action taken by the Investigator must be documented:

***a) General actions taken in the event of an AE***

- None
- Medication (other than IMP) or other (e.g., physical) therapy started
- Test performed
- Other (to be specified)

***b) IMP-related actions taken in the event of an AE***

- None
- Product withdrawn
- Dose reduced
- Dose increased

The Investigator will follow up on each AE until it has resolved or until the medical condition of the subject/patient has stabilised. Any relevant follow-up information will be reported to the Sponsor.

### 7.3.3 Serious Adverse Events (SAEs)

A **serious AE (SAE)** is any untoward medical occurrence that at any dose:

- results in death,
- is life-threatening (see below),
- requires hospitalisation or prolongation of existing hospitalisation,
- results in persistent or significant disability/incapacity,
- is a congenital anomaly/birth defect,
- is another important medical event.

**NOTE:** The term 'life-threatening' refers to an event in which the subject/patient was, in the view of the reporting Investigator, at immediate risk of death at the time of the event; it does not refer to an event which may hypothetically have caused death had it been more severe.

In deciding whether an AE/ADR is serious, medical judgment should be exercised. Thus, important AEs/ADRs that are not immediately life-threatening or do not result in death or hospitalisation but may jeopardise the subject/patient or may require intervention to prevent one of the other outcomes listed in the definitions above should also be considered serious.

In addition, although not classified under the seriousness criteria, all suspected transmissions of an infectious agent should be reported as SAE. A suspected virus transmission means that virus antigen has been detected in the patient. A passive transmission of antibodies alone does not constitute a suspected virus transmission.

### 7.3.4 SAE Reporting Timelines

All SAEs, whether or not they are suspected to be related to study treatment, are to be reported immediately by telephone, fax, or email to the Clinical Project Manager or designee.

The contact details will be communicated at the study initiation visit.

In addition, within 24 hours after recognition of the event, an Octapharma Serious Adverse Event Report must be completed and submitted to:

### **Waivers the from SAE Reporting Requirement**

Waivers from the SAE reporting requirement include:

- hospitalizations due to infusions on consecutive days (e.g. for subjects with long travel hours);
- surgeries that are elective or were planned before study entry;
- prolongation of existing hospitalizations for economic or social, but not medical, reasons.

Such hospitalizations, surgeries, or prolongation of hospitalizations should not be considered SAEs.

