Although a spectrum of severity exists for DM, this entity is more likely to be associated with rapid and aggressive myositis. DM is seen in both, children and adults, and the early symptoms include distinct skin manifestations accompanying or preceding muscle weakness. The classic skin manifestations include periorbital heliotrope (blue-purple) rash with edema; erythematous rash on the face, knees, elbows, malleoli, neck, anterior chest (in a V-sign), and back and shoulders (in a shawl sign); and a violaceous eruption (Gottron's rash) on the knuckles, which may evolve into a scaling discoloredation. The lesions are photosensitive and may be aggravated by ultraviolet radiation.

The risk of cancer is increased in adults during the first 3-5 years after the onset of DM, with a reported frequency of 9-32%; necessitating a thorough annual workup in the first 3 years after disease onset. The most common forms are ovarian, breast, and colon cancer, melanoma, and non-Hodgkin's lymphoma.

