#### 7.3.2.2 Collection of AEs

The condition of the subject/patient will be monitored throughout the study. At each visit, whether scheduled or unscheduled, AEs will be elicited using a standard non-leading question such as "How have you been since the last visit/during the previous study period?" AEs should be registered starting from the first dose of IMP (start of first injection).

In addition, the Investigator will check the subject/patient diaries (if applicable) for any documented event.

Local injection site reactions are to be assessed by both patients and investigators.

Patients have to grade the overall perception of local reactions in their diaries at 24 hours ( $\pm 3$  hours) post-infusion session using a 4-point rating scale: 0=none, 1=mild, 2=moderate, 3=severe.

Investigators have to evaluate local reactions at approximately 1 hour post-infusion session at every study site visit, using the same 4-point rating scale: 0=none, 1=mild, 2=moderate, 3=severe.

Local infusion site reactions will be noted on the adverse event pages in the CRF.

Any AE or ADR occurring during the study will be noted in detail on the appropriate pages of the eCRF. If the subject reports several signs or symptoms representing a single syndrome or diagnosis, the diagnosis should be recorded in the eCRF. The Investigator will grade the severity of all AEs or ADRs (mild, moderate, or severe), the seriousness (non-serious or serious), and the causality as defined in **Sections 7.3.2.3, 7.3.2.4, and 7.3.3**. The Sponsor is responsible for assessing the expectedness of each ADR (expected or unexpected) as defined in **Section 7.3.2.5**.

In the event of clinically significant abnormal laboratory findings, the tests will be confirmed and the patient followed up until the laboratory values have returned to normal and/or an adequate explanation for the abnormality has become available.

Diseases, signs and symptoms, and/or laboratory abnormalities already present before the first administration of IMP will not be considered AEs unless an exacerbation in intensity or frequency (worsening) occurs.

The Investigator will provide detailed information about any abnormalities and about the nature of and reasons for any action taken as well as any other observations or comments that may be useful for the interpretation and understanding of an AE or ADR.

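### The SAE waiver exempts any elective surgery, so an admission for a condition that began or worsened on treatment can go unreported as serious

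*Protocol*

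**What the plan says.** Protocol 7.3.3 lists the seriousness criteria. One is that the event "requires hospitalisation or prolongation of existing hospitalisation". The same section adds that important events which may jeopardise the patient, or which "may require intervention to prevent one of the other outcomes listed in the definitions above should also be considered serious", count as well.

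Protocol 7.3.4 sets the reporting rule: "All SAEs, whether or not they are suspected to be related to study treatment, are to be reported immediately". A written SAE report must follow within 24 hours of recognising the event.

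The waiver list after 7.3.4 has three items. The surgical one reads "surgeries that are elective or were planned before study entry". The list closes with: "Such hospitalizations, surgeries, or prolongation of hospitalizations should not be considered SAEs".

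Protocol 7.3.2.2 governs adverse events in general. "Diseases, signs and symptoms, and/or laboratory abnormalities already present before the first administration of IMP will not be considered AEs", unless they worsen. For everything else, "Any AE or ADR occurring during the study will be noted in detail on the appropriate pages of the eCRF", and the investigator grades its seriousness.

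SAP 11.1 tabulates the incidence and number of SAEs. The SAP has no SAE definition of its own and no step that brings waived cases back.

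**The concern.** A waiver for surgery already scheduled at study entry is sound, because such an operation says nothing about what happened on treatment. The word joining the two alternatives goes further. The time limit attaches only to the second alternative, so being elective is enough for the waiver to apply, whenever the operation was arranged and for whatever reason.

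The other two waiver items are each tied to a cause unrelated to a new medical problem: infusion logistics, and stays prolonged for non-medical reasons. The surgical item has no such tie. An admission for scheduled surgery on a new or worsened condition therefore satisfies 7.3.3 and is ruled out by the waiver.

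What is at stake is the completeness of expedited SAE reporting, of the SAE table in SAP 11.1, and of the SAE narratives (SAP 11.1) and detailed SAE descriptions (Protocol 9.9). Safety and tolerability is a stated secondary objective. With about 45 sites, the same event could also be classified differently from one site to another.

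**Working it through.** The plan states no figure on this point, so the check is to take each kind of surgical admission through the rules in order: is it an adverse event under 7.3.2.2, is it serious under 7.3.3, and does the waiver remove it?

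1. **Surgery planned before entry, condition unchanged.** Not an adverse event under 7.3.2.2. The second alternative waives it. Nothing is lost.
2. **Elective surgery arranged after entry, pre-existing condition unchanged.** Again not an adverse event. The first alternative waives it. Nothing is lost.
3. **Surgery for a pre-existing condition that worsened after the first infusion.** The worsening is an adverse event, and the admission meets 7.3.3. The waiver removes it if the operation is elective. It also removes it if the operation had been planned before entry, because that alternative has no proviso about worsening either.
4. **Elective surgery for a condition that first arose after the first infusion.** An adverse event, and the admission meets 7.3.3. The first alternative waives it.
5. **Emergency surgery for a new condition.** Not elective and not pre-planned, so not waived. It is an SAE.

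The conflict is confined to cases 3 and 4. Cases 1 and 2 are already kept out by 7.3.2.2, so for them the waiver only confirms the existing rule.

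Within cases 3 and 4, the event leaves the SAE data only if all of the following hold:

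- the waived admission is its only seriousness criterion, so it is not fatal, life-threatening or disabling and meets no other criterion in 7.3.3;
- it is not a thromboembolic event or a hemolytic transfusion reaction, which Protocol 7.3.5 requires to be reported as SAEs in any case;
- the investigator does not judge it an important medical event.

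**Size.** The documents give neither an elective-surgery rate nor an SAE rate, so the expected number of lost events cannot be computed. For scale only: with the planned 39 patients per arm, one patient whose only SAE is waived lowers that arm's SAE incidence by 1/39 = 2.6 percentage points. This is the weight of one patient, not an estimate of the effect, and it is zero if the patient has another SAE.

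**The case against.** The strongest reply is that the closing line of the waiver names hospital stays and operations and does not mention the underlying condition. On that reading the waiver covers the procedure, the diagnosis is entered in the eCRF, and its seriousness is graded in the usual way. This is a fair reading and probably the intended one. However, the text does not say so, and it does not say whether a waived admission may still serve as the hospitalisation criterion for the diagnosis behind it. A site that follows the list literally would conclude that it may not.

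Three stronger readings are tempting, and the documents do not support them.

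- **That such events disappear from the safety data, or that the important-medical-event clause is the only way back.** They stay in the adverse event data. The other criteria in 7.3.3 and the rule in 7.3.5 also apply.
- **That a tumour found on study and resected electively would be missed.** It fits the important-medical-event wording in 7.3.3 directly and would probably be reported. Malignancy is also an exclusion criterion, and Protocol 4.3.1 lists a disease of that kind as a possible reason for stopping. If the patient is withdrawn, the case also appears among withdrawals and among adverse events leading to withdrawal.
- **That the loss can be sized from Protocol 1.2.** That section says "The risk of cancer is increased in adults during the first 3-5 years after the onset of DM" and gives a reported frequency of 9-32%. This is not a hazard for the trial population, which excludes cancer-associated myositis and recent malignancy. It counts cancers, not elective operations and not lost SAEs.

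Nor is bias between arms shown: the study is blinded and the waiver applies equally to both arms.

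**Conclusion.** The point holds as a wording defect with limited reach. The waiver's first alternative is unrestricted and contradicts the hospitalisation criterion for surgery on conditions that arise or worsen on treatment. The effect is on SAE reporting and SAE counts, and only for events with no other route to seriousness. The number is unknown and probably small. The primary endpoint, the stopping rules for thromboembolic and hemolytic events, and the general adverse event tables are not affected.

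The conclusion rests on the literal reading of the waiver and on there being no clarification elsewhere. A short stretch of text between the reporting timelines in 7.3.4 and the waiver list was not available for this check, nor was any separate SAE completion guidance.

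**What to change.** Reword the surgical item so that it covers operations planned before study entry, or elective operations for a pre-existing condition, in both cases provided that the condition has not worsened since the first IMP infusion. This keeps the waiver for harmless operations scheduled after entry for an unchanged condition.

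Add one sentence stating that the waiver applies to the procedure only, and that any new or worsened condition leading to surgery is assessed against the criteria in 7.3.3.

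The cost is one item and one sentence in the protocol, the same change in any SAE guidance given to sites, and possibly a few more SAE reports. The analysis methods in the SAP need no change.

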### 7.3.5 Adverse Events of Special Interest (AESI)

The following AEs are defined as AESI:

- thromboembolic events (TEEs);
- hemolytic transfusion reactions (HTRs).

For these AESI, the general definitions and procedures that are described elsewhere in Section 7.3 apply as well, and they must be reported as SAEs. Premature termination criteria related to AESI are defined in Section 6.2.3.1. The IDMC will review all AESI in real time through an electronic system to be set up by the sponsor.

#### 7.3.5.1 Thromboembolic Events (TEEs)

There is clinical evidence of an association between IgG administration and TEEs such as ischemic stroke, transient ischemic attack, cerebral infarction, cerebrovascular accident, cerebral thrombosis, embolic infarctions, [acute] myocardial infarction, deep vein thrombosis (DVT), pulmonary embolism (PE), venous thrombosis.

TEEs will be monitored as follows:

- Wells criteria for assessment of probability for possible DVTs at each visit [40] modified according to NICE Clinical Guideline 144, 2012]:

Present	Score
 Active cancer (treatment ongoing, within 6 months, or palliative)	+1
 Paralysis, paresis or recent plaster immobilization of the lower extremities	+1
 Recently bedridden for 3 days or more or major surgery within 12 weeks requiring general or regional anesthesia	+1
 Localized tenderness along the distribution of the deep venous system	+1
 Entire leg swollen	+1
 Calf swelling at least 3 cm larger than asymptomatic side	+1
 Pitting edema confined to the symptomatic leg	+1
 Collateral superficial veins (non-varicose)	+1
 Previously documented DVT*	+1
 An alternative diagnosis is at least as likely as DVT	-2
Clinical Probability Simplified Score	DVT likely $\geq 2$ points DVT unlikely $\leq 1$ point

\*Note: This is also an exclusion criterion.

- If the Well's DVT probability score is  $\geq 2$ , then a Doppler screening for DVT will have to be completed (recommended: Doppler using color duplex sonography) and a blood sample will have to be taken for D-dimers.

- Wells criteria for assessment of probability for possible PE at each visit [41]; modified according to NICE Clinical Guideline 144, 2012]:

Present	Score
 Clinical signs and symptoms of DVT (minimum of leg swelling and pain with palpation of the deep veins)	3
 An alternative diagnosis is less likely than PE	3
 Heart rate > 100 beats per minute	1.5
 Immobilization for more than 3 days or surgery in the previous 4 weeks	1.5
 Previous DVT/PE	1.5
 Hemoptysis	1
 Malignancy (on treatment, treated in the last 6 months, or palliative)	1
Clinical Probability Simplified Score	
	PE likely >4 points
	PE unlikely ≤4 point

\*Note: This is also an exclusion criterion.

Therapeutic measures managing suspected TEEs shall be initiated according to local clinical practice (e.g. anticoagulation).

#### 7.3.5.2 Hemolytic Transfusion Reactions (HTRs)

HTRs can develop subsequent to immunoglobulin therapy. Immunoglobulin-related hemolysis is associated with passive transfer of anti-A and anti-B hemagglutinins.

HTRs will be monitored as follows at pre-defined visits (see Flowchart of Study Events):

- Direct Coombs' test. If a positive result is obtained, the antibodies responsible for the positive test result will be eluted to investigate their specificity (anti-A, anti-B or anti-D).
- Other safety lab parameters: hemoglobin, serum haptoglobin, plasma-free hemoglobin, LDH.
- Urinalysis parameters.

Intravascular hemolysis will be suspected if all of the following criteria are fulfilled (modified acc. to FDA Guidance for Industry 2008):

- a positive direct Coombs' test result;
- a drop in hemoglobin of 2 g/dL or greater;
- a drop in serum haptoglobin to below the lower limit of normal;
- a rise in serum LDH from baseline.

In case of a patient's positive direct Coombs test the investigator has to check if the above mentioned criteria are fulfilled. The results of these additional tests and any clinical signs or symptoms potentially related to hemolysis will be documented in the patient's medical record.

 Guidance for Industry. Safety, Efficacy, and Pharmacokinetic Studies to Support Marketing of Immune Globulin Intravenous (Human) as Replacement Therapy for Primary Humoral Immunodeficiency. 2008

Therapeutic measures managing suspected HTRs shall be initiated according to local clinical practice.

### 7.3.6 Laboratory Tests

The following laboratory parameters will be investigated during the study at the time points specified in Section 6.1.

#### 7.3.6.1 Central Laboratory

The following laboratory tests will be done at a central laboratory:

Clinical chemistry: Na+ (sodium), K+ (potassium), glucose, ALAT, ASAT, LDH, total bilirubin, BUN (blood urea nitrogen) or urea, creatinine, albumin.

Hematology: hematocrit, hemoglobin, complete blood count with differential (red blood cell counts, white blood cell counts [neutrophils, eosinophils, basophils, lymphocytes, monocytes], platelets).

Additional safety laboratory parameters:

serum haptoglobin and plasma-free hemoglobin.

Direct Coombs' test: if positive, the antibodies responsible for the positive Coombs' test will be eluted to investigate their specificity (anti-A, anti-B or anti-D).

D-dimers.

Serum IgG.

Enzymes: aldolase, creatine kinase and, if clinical chemistry will be performed by a local laboratory, ALAT, ASAT and LDH. For the CSM only values measured in the central laboratory will be used.

Viral markers: details see Section 7.3.7.

Pregnancy test: in blood if not performed locally.

Urinalysis: protein, glucose, pH, nitrite, ketones, leukocytes, hemoglobin, bilirubin, urobilinogen, and urine hemosiderin.

Blood and urine sampling will take place according to the time points given in Section 6.1. The methods used for each parameter and the normal ranges of each determination will be provided in the Clinical Study Report. A lab manual detailing blood and urine sampling and shipment procedures will be provided to each study site.

#### 7.3.6.2 Local Laboratory

The following laboratory tests will in some countries be done by the local laboratories of each study site:

- Hematology: hematocrit, hemoglobin, complete blood count with differential (red blood cell counts, white blood cell counts (neutrophils, eosinophils, basophils, lymphocytes, monocytes), platelets).
- Chemistry: Na+ (sodium), K+ (potassium), glucose, ALAT, ASAT, LDH, total bilirubin, BUN (blood urea nitrogen) or urea, creatinine, albumin.
- Pregnancy test: either in urine or in blood.

- Urinalysis: protein, glucose, pH, nitrite, ketones, leukocytes, hemoglobin, bilirubin, urobilinogen, and urine hemosiderin.

The methods of determination and normal ranges for each parameter will be provided in the clinical study report.

